**Visit 5 (90 days post cataract surgery +/- 14 days)**

- OSDI
- VAS
- NITBUT
- TMH
- Manifest refraction
- UCDVA/BCDVA measured by ETDRS
- Slit lamp exam
- Corneal fluorescein staining
- Intraocular pressure measured by standard of care
- Adverse events will be collected

**Data Analysis and Data Monitoring**

Data will be captured by the principal investigators, sub-investigators and study coordinators. Data will be documented on source documents and subjects will be identified by subject numbers.

Data analysis will occur on an excel spreadsheet or in R statistical software with subjects identified by subject number. The Excel spreadsheet or R scripts will be on computer(s) that are password protected.

Baseline demographic and ocular characteristics will be quantified using descriptive statistics. Statistical analysis will be completed on all primary and secondary endpoints. A primary analysis will be conducted upon completion of the 3-month study period with an interim analysis of the first 30 patients to complete all visits.

The planned sample size is 60 eyes of 60 patients, with the primary eye selected as the eye with lower NITBUT at screening. Sample size was calculated to provide 80% power to detect a meaningful change of 0.8 seconds or greater from baseline to 3-months in NITBUT.

Secondary analyses will include fellow eyes and all (primary + fellow) eyes.

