Fortunately, the dry eye treatment landscape continues to evolve which enables more individualized care for patients. Recently, a cross-linked hyaluronic acid canalicular gel (Lacrifill®) was introduced, which represents a novel, alternative solution for lacrimal occlusion. This treatment works by occluding the tear drainage system, thereby increasing the retention of natural tears, improving tear film stability, and reducing ocular surface irritation. Proactive use of the canalicular gel could lead to more reliable pre-operative measurements, better visual outcomes, and increased post-operative comfort, which is particularly important for

patients receiving advanced technology IOLs. Improvements in both signs and symptoms of DED have been reported using lacrimal occlusion, suggesting it could play a valuable role in optimizing the cataract surgery experience.

**Study Design:** Prospective, single-site, single-arm study enrolling 60 patients who have elected advanced IOL implantation at the time of cataract surgery and have a diagnosis of dry eye disease. The study will consist of 5 study visits, over a 3-5 month time period. Patients will receive bilateral lacrimal occlusion of crosslinked hyaluronate canalicular gel pre-operatively

The primary endpoint will be the change from baseline to 3- month visit in non-invasive tear break up time (NITBUT) in primary eyes as measured by a non-invasive, automated ocular surface analyzer. Additional endpoints measured will be the change from baseline in the visual analog score and OSDI. The effect of pre-operative lacrimal occlusion on accuracy of preoperative biometry/keratometry measurements will be evaluated as well as residual refractive error at 30 and 90 days post-operative.

**Subject Population:** 60 subjects, who have elected bilateral refractive cataract surgery will be enrolled.

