**Data Storage and Confidentiality**

Private information and your medical record will be shared with individuals and organizations that conduct or watch over this research, including:

- The research sponsor
- People who work with the research sponsor
- The Institutional Review Board (IRB) that reviewed this research

We may publish the results of this research. However, we will keep all names and other identifying information confidential.

We protect all information from disclosure to others to the extent required by law. We cannot promise complete secrecy.

Sources documents will be placed in a binder and stored in locked cabinets. This trial will be conducted in compliance with the protocol, GCP, and applicable regulatory requirement(s).

The participation for this trial is voluntary and subjects may stop or withdraw during the one-time examination at their discretion.

The principal investigator will report to the IRB any changes in research activity, serious adverse events, and completion of the study.

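### Do the interim look at 30 completers and the enrolment of exactly 60 patients break the error rate or the stated 80% power?

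*Protocol*

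**What the plan says.** The primary endpoint is a within-eye change in a single-arm study: "The primary endpoint will be the change from baseline to 3- month visit in non-invasive tear break up time (NITBUT) in primary eyes". Under Data Analysis and Data Monitoring, the Protocol sets one primary analysis at the end of the three-month period, "with an interim analysis of the first 30 patients to complete all visits". The sentence before it reads "Statistical analysis will be completed on all primary and secondary endpoints".

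On size, the same section says "The planned sample size is 60 eyes of 60 patients" and "Sample size was calculated to provide 80% power to detect a meaningful change of 0.8 seconds or greater from baseline to 3-months in NITBUT". The Synopsis, under Subject Population, says "60 subjects, who have elected bilateral refractive cataract surgery will be enrolled".

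The Protocol gives no significance level, sidedness, standard deviation of the change or attrition rate. It does not say what the interim is for, or that anything can be stopped or claimed on it.

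**The concern.** Patients who have finished all visits have their 90-day NITBUT, so the interim has the primary endpoint to hand at half the planned information (30/60). It is mentioned in the same sentence as the primary analysis. The Protocol calls its baseline summaries descriptive but does not say that of the interim. In a single-arm study with no independent monitoring body described, a reader could fear that an interim p-value below 0.05 would be presented as the result, and that a second test at 60 would then push the error rate above its nominal level.

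The power statement raises a separate worry. If 60 is the calculated number and also the number enrolled, patients lost over three to five months of visits would take the study below 80%. Withdrawal is allowed for ("subjects may stop or withdraw during the one-time examination at their discretion"), but no allowance for it is stated.

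**Working it through.** **Inputs from the Protocol:** n = 60 primary eyes, one per patient; 80% power; change of 0.8 s; one interim at 30 completers.

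**Assumptions, not in the Protocol:** two-sided alpha of 0.05; the SD of the change; loss of 5% to 15%.

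**1. The plan's own figure.** For a one-sample test of a paired change, n = (SD × (z for alpha + z for power) / change)². Without SD and alpha, n = 60 cannot be reproduced. It can only be solved backwards:

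- Normal formula: SD = 0.8 × √60 / (1.960 + 0.842) = 2.21 s.
- Noncentral t: SD = 2.18 s.
- One-sided 0.05: SD = 2.49 s (normal) or 2.46 s (t).

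So 60 is consistent with 80% power over a range of unstated inputs.

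**2. Error rate with two unadjusted looks.** The two test statistics are correlated √(30/60) = 0.707. Under the null, the probability that either exceeds 1.96 in absolute value is 0.0831, or 8.3%. This needs three things together: a test at the interim, the same 0.05 level at both looks, and a claim allowed at either. If the study always continues to 60 and the claim rests only on the final test, that test keeps its 5% level whatever was seen at 30.

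**3. Effect of the look on power.** With all 60 evaluable and the SD from step 1:

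| Rule | Type I error | Power |
|---|---|---|
| Single final test | 5.0% | 80.0% |
| Two looks at 0.05 | 8.3% | 82.1% |
| O'Brien-Fleming (p < 0.0052, then p < 0.048) | 5.0% | 79.7% |
| Haybittle-Peto (p < 0.001, then p < 0.05) | 5.02% | 80.0% |

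An unadjusted look does not lower power, and these two boundaries cost at most 0.3 points. The size of the study does not depend on how the interim is handled.

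**4. Power after losses** (noncentral t, single final test, two-sided 0.05):

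| Evaluable eyes | Loss from 60 | SD 2.18 s | SD 2.0 s |
|---|---|---|---|
| 60 | 0% | 80.0% | 86.2% |
| 57 | 5% | 77.9% | 84.3% |
| 54 | 10% | 75.6% | 82.3% |
| 51 | 15% | 73.1% | 80.0% |

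The SD 2.18 s column starts at 80% by construction, so any loss must show as a shortfall. With SD 2.0 s, 60 already covers a 15% loss. In the other direction, SD 2.5 s would give 68.4% at 60 eyes under two-sided 0.05, although a design SD near that value fits the stated 80% if the test is one-sided at 0.05. The Protocol does not say which case applies.

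**The case for a change.** The strongest argument for a change is that the Protocol itself fixes the look, its timing and its population, so whether that look can support a claim is a design decision and not a detail for later. The remedy is also cheap: one sentence calling the interim descriptive, or a boundary costing 0.3 points of power. The plain reading of a planned size calculated for 80% power is that 60 is the number needed, and nothing says it includes an allowance for loss.

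Part of this stands. The interim's purpose is unstated, the planned and enrolled numbers are the same, and the 80% figure cannot be checked from the Protocol. An inferential reading of the interim is possible. But it has to be supplied by the reader, because the text places the single primary analysis at completion and gives the interim no decision to make. The Protocol also does not say who analyses the data, so an early claim by the investigators is conjecture. Interim error control, the SD and alpha behind the sample size, and the handling of losses are matters that a statistical analysis plan commonly covers, and one may exist here.

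**Conclusion.** The concern does not hold as a defect of the Protocol. The arithmetic is right, but both figures are conditional. The 8.3% requires unadjusted tests at an assumed two-sided 0.05 with success claimable at either look. The fall to about 78% to 73% requires that 60 be the evaluable number needed, an SD near 2.18 s and an assumed 5% to 15% loss. The Protocol states none of these conditions, and at SD 2.0 s the 80% survives a 15% loss. A sponsor who follows the text as written, with one primary analysis at completion, has a valid final test. What is left is a gap that analysts can sensibly fill by treating the interim as descriptive and recording the SD, alpha and expected evaluable number in the analysis plan.

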**Inclusion criteria:**

1. Be willing and able to understand and sign the informed consent form (ICF)
2. Men or non-pregnant women age 22 or older
3. Clear intraocular media other than cataract
4. Diagnosis of dry eye disease (OSDI score  $\geq 13$ )
5. Non-invasive Tear break up time  $\leq 10$  seconds in at least one eye
6. Willing and able to comply with all study related visits and procedures
7. In the opinion of the investigator, patients who are appropriate for advanced technology lens implants

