**Visit 0 (7 to 45 days prior to surgery):**

- Informed consent will be obtained prior to collection of any study-specific data.
- Potential subjects' demographics, medical and ocular history, and concomitant medications will be reviewed.
- Inclusion and exclusion criteria will be reviewed for each subject.
- Ocular Surface Disease Index (OSDI) will be obtained
- Visual Analog Score will be obtained

- Pre-operative biometry measurements will be obtained
- Non-invasive tear break up time (NITBUT) will be obtained
- Automated tear meniscus (TMH) will be obtained
- Best-corrected distance visual acuity (BCDVA) will be obtained using the ETDRS
- Slit Lamp Exam
- NaFl staining will be measured (NEI grading scale)
- If both eyes qualify for the study, the primary eye will be the eye with the smaller NITBUT. If the NITBUT is the same in both eyes, the primary eye will be the right eye.
- Lacrimal occlusion of the inferior canaliculi of both eyes will be performed

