**Visit 1A/B (operative day[s]):**

- Repeated biometry measurements obtained on each eye
- VAS
- Patients may undergo sequential bilateral surgery per site standard of care
- Adverse events will be collected

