**Visit 3 (7 days post cataract surgery +/- 2 days)**

- OSDI
- VAS
- NITBUT
- TMH
- Manifest refraction
- UCDVA/BCDVA measured by ETDRS
- Slit lamp exam
- Corneal fluorescein staining
- Intraocular pressure measured by standard of care
- Adverse events will be collected

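### One Visit 0 NITBUT measurement qualifies the patient, picks the worse eye and serves as baseline, so selection alone pushes the single-arm primary change toward improvement by an unknown amount

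*Protocol*

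**What the plan says.** - **Endpoint** (Protocol, Synopsis, Study Design): "The primary endpoint will be the change from baseline to 3- month visit in non-invasive tear break up time (NITBUT) in primary eyes". The study is single-arm with 60 patients.
- **Eligibility** (Inclusion criteria): an NITBUT of 10 s or less, "seconds in at least one eye".
- **Visit 0:** "Non-invasive tear break up time (NITBUT) will be obtained". If both eyes qualify, "the primary eye will be the eye with the smaller NITBUT". At the same visit, "Lacrimal occlusion of the inferior canaliculi of both eyes will be performed".
- **Visit 1A/B (operative day):** "Repeated biometry measurements obtained on each eye", together with the VAS. NITBUT is not listed here or at Visit 2.
- **Next NITBUT:** "Visit 3 (7 days post cataract surgery +/- 2 days"), after both gel and surgery.
- **Data Analysis and Data Monitoring:** 60 eyes of 60 patients, "with the primary eye selected as the eye with lower NITBUT at screening". The sample size is said to give 80% power for a 0.8 s change. Fellow-eye and all-eyes analyses are planned as secondary.

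The protocol does not formally define baseline, but no NITBUT other than the Visit 0 one is scheduled before treatment. It does not say how many captures make up that measurement.

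**The concern.** One visit's measurement does three jobs: it admits the patient, selects the eye and supplies the starting value. Any measurement error makes the lower of two readings too low on average, and the 10 s ceiling adds to this. The next reading carries fresh error, so the expected change is positive even if nothing has changed. This is regression to the mean.

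With a concurrent control the artefact would appear in both arms and cancel. Here it goes straight into the primary estimate, mixed with any benefit, and the primary analysis alone cannot separate the two. A later analysis plan could add a caution or an adjustment. It could not supply a pre-gel reading that was never taken.

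**Working it through.** **Inputs from the protocol:** n = 60, power 80%, target change 0.8 s, entry at 10 s or less in at least one eye, primary eye = lower reading. SD of change, alpha, dropout, repeatability and between-eye correlation are not stated.

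**Step 1: the plan's own figure.** N = 60 cannot be reproduced without an SD, only back-solved. Assuming a two-sided 0.05 paired test:

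SD = 0.8 × √60 / (1.960 + 0.842) = 6.197 / 2.802 = 2.21 s

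The noncentral t gives 2.176 s, which is used below. A one-sided 0.05 test would imply 2.46 s.

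**Step 2: the effect of picking the lower eye, by hand.** Let σe be the eye-specific error SD of one measurement and τ the SD of the true difference of each eye from its patient's mean. With no true change and no entry limit, the expected rise in the lower eye is

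σe² / √(π(τ² + σe²))

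This is positive whenever σe > 0. For example, if a quarter of the variance of change is eye noise, σe² = 0.25 × 2.176² / 2 = 0.592. With τ = 1 s the rise is 0.592 / √(π × 1.592) = 0.592 / 2.236 = 0.26 s. The entry limit adds to this.

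**Step 3: both selections together, by simulation.** All of these are assumptions:
- true mean 6, 8 or 10 s; between-patient SD 2 or 3 s; τ 0.5, 1 or 1.5 s (18 combinations)
- six splits of the variance of change into eye noise, session noise shared by both eyes, and true heterogeneity
- zero mean change; 300,000 patients per scenario

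P is the chance that the paired t-test on 60 eyes declares improvement; without bias it is 2.5%. Ranges run over the 18 combinations.

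| Eye noise / shared noise / heterogeneity (%) | Rise in primary eye (s) | P | Residual rise, same-session second baseline (s) | Residual rise, both-eye mean (s) |
|---|---|---|---|---|
| 5 / 15 / 80 | 0.06–0.26 | 4–14% | 0.01–0.12 | 0.00–0.14 |
| 10 / 10 / 80 | 0.09–0.32 | 5–20% | 0.01–0.08 | 0.01–0.13 |
| 25 / 25 / 50 | 0.23–0.65 | 12–65% | 0.02–0.18 | 0.02–0.26 |
| 33 / 33 / 33 | 0.29–0.80 | 17–83% | 0.02–0.22 | 0.03–0.33 |
| 50 / 50 / 0 | 0.41–1.07 | 32–98% | 0.03–0.31 | 0.05–0.46 |
| 100 / 0 / 0 | 0.65–1.20 | 67% to nearly 100% | about 0 | 0.02–0.29 |

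Hand check of one P: a rise of 0.32 s gives 0.32 × √60 / 2.176 = 1.14 standard errors. The critical value is about 2.00, so P is roughly the normal tail beyond 0.86, about 20%.

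With a second baseline from a separate session, the rise is within 0.01 s of zero in every split and P is 2.3–2.7%. Fellow eyes change by −0.81 to +0.06 s: they mostly move the opposite way, as expected if eye-picking is at work.

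**Step 4: sensitivity to the model.** The normal model puts up to 9% of lower-eye readings below zero in its worst combinations. It was therefore repeated with log-normal levels and error proportional to the reading. The primary-eye rise, by what the 2.18 s SD is taken to describe, is:

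| Split | SD in an unselected eye (s) | SD in primary eyes (s) |
|---|---|---|
| 80% heterogeneity | 0.05–0.28 | 0.08–0.36 |
| Quarter to a third eye noise | 0.18–0.69 | 0.29–0.90 |
| All eye noise | up to 1.04 | up to 1.39 |

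**The case against.** - **The size is not supported by the document.** This stands. The SD is back-solved from an assumed test, and the upper ends come from a source population whose mean equals the 10 s limit. With means of 6–8 s only, the rise is 0.06–0.24 s at 80% heterogeneity, 0.22–0.58 s at a quarter to a third eye noise, and 0.41–0.79 s at half eye and half shared noise. Averaging several captures would also move the trial toward the low end. None of this changes the sign.
- **Surgery may act the other way.** The Background says surgery can worsen dry eye, and every 3-month reading follows surgery. The net observed change therefore need not be positive, and zero net change is a benchmark, not a forecast. But a surgical effect is a real change whose cause is in question. It does not remove the selection artefact from the measured change.
- **Choosing the worse eye is a legitimate design.** Agreed. The difficulty is reusing the selecting measurement as baseline with no control.
- **Fellow-eye and all-eyes analyses are already planned.** They would help to expose the artefact, but they are secondary and the headline result rests on the lower eye.

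**Conclusion.** The concern holds. Mechanism and direction follow from the visit schedule, the eye-selection rule and the single arm, and need only some measurement error in NITBUT. Confidence is high on those points and does not extend to the size.

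The artefact may be a small part of the 0.8 s target (0.06–0.32 s if most of the variance is true heterogeneity) or most of it (up to 0.80 s if a third is eye noise). Larger values need little or no true heterogeneity in the normal model, or the positive-only model with the SD read as that in primary eyes. The grid is a range of assumptions, not a probability statement. This should be fixed before further patients are treated, because an unselected baseline cannot be recovered once the gel is in place.

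**What to change.** **Main change.** Before the gel is placed, take a further automated NITBUT in both eyes that plays no part in eligibility or eye selection. Define it as the baseline for the primary change. The worse-eye question is kept.

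- *Separate session:* removes the bias (0.00 ± 0.01 s). It may need an extra visit, with consent taken first.
- *Same session:* adds a few minutes and removes the eye-specific part. Shared session noise of 0.00–0.31 s remains (at most 0.12 s at 80% heterogeneity; up to 0.38 s in the positive-only model).

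Either way a short amendment is enough. The lower-eye analysis keeps 80–81% power for 0.8 s at n = 60, although the apparent effect will probably be smaller.

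**Fallback if no further reading is taken.** Make the planned all-eyes analysis primary, as the per-patient mean change over both eyes. Report the lower-eye result as secondary with a stated regression-to-the-mean caution. This needs no new data and has less bias than the current primary analysis in every normal-model scenario. It is a trade-off, not an equivalent:

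- 0.00–0.46 s remains (up to 0.57 s in the positive-only model).
- The question moves from the worse eye to the patient.
- Fellow eyes above 10 s (2–52% of fellow eyes in these scenarios) may dilute a true effect.
- Its 81–98% power holds only if the full 0.8 s occurs in both eyes.

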**Data Storage and Confidentiality**

Private information and your medical record will be shared with individuals and organizations that conduct or watch over this research, including:

- The research sponsor
- People who work with the research sponsor
- The Institutional Review Board (IRB) that reviewed this research

We may publish the results of this research. However, we will keep all names and other identifying information confidential.

We protect all information from disclosure to others to the extent required by law. We cannot promise complete secrecy.

Sources documents will be placed in a binder and stored in locked cabinets. This trial will be conducted in compliance with the protocol, GCP, and applicable regulatory requirement(s).

The participation for this trial is voluntary and subjects may stop or withdraw during the one-time examination at their discretion.

The principal investigator will report to the IRB any changes in research activity, serious adverse events, and completion of the study.

